#### *3.5.1 Analysis of Efficacy*

Study data will be summarized by treatment group using descriptive statistics, figures, and/or raw data listings where appropriate.

##### *3.5.1.1 Primary Efficacy Analysis*

For each treatment group, descriptive statistics will be calculated at each visit for amount of food (weight and energy content) consumed during lunch.

Observed values will be analyzed using a mixed model of repeated measures approach using a significance level of  $\alpha = 0.1$ . Fixed effects for the model will be treatment, visit, and treatment-by-visit interaction with a random effect for subject. Least squares mean values, differences in least squared means values, standard errors, p-values, and 90% confidence intervals will be presented.

##### *3.5.1.2 Secondary Efficacy Analysis*

Observed values and change from baseline values of hunger, satiety, prospective consumption, desire to eat, and palatability (tastiness) scores on a VAS (0 to 100 mm) will be summarized using descriptive statistics for all measured visits and timepoints.

The area under effect (AUE) will also be calculated from time 0 to 6.5 hours (390 minutes) for each VAS scale, except palatability, on Day 1 and Day 7.  $AUE_{0-6.5}$  will be calculated using the trapezoid method. If any observations are missing for the scheduled timepoints for the AUE calculation, the missing values will be imputed using the last observation carried forward (LOCF) method.

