### **1.3 Clinical Summary**

The recombinant version of ROSE-010 (LY307161) has been tested in 3 clinical studies. Two Phase 1 clinical studies were conducted to evaluate safety and PK; 1 in healthy subjects, and 1 in T2DM patients. A Phase 2a efficacy study (GL61-001) for the treatment of pain of IBS has been performed in Europe.

LY307161 was generally safe and well tolerated when administered SC in early human clinical studies. Nausea and vomiting were observed as the consistent dose-related side effects of LY307161. Although the majority of subjects tolerated all doses, doses of 500 mcg and greater produced nausea and/or vomiting in the majority of subjects. The maximum tolerated dose was therefore determined to be 400 mcg.

The most frequent adverse events (AEs) in single and multiple dose studies were nausea and vomiting, which occurred at time to peak concentration. These AEs were considered to be dose-related and were of short duration, suggesting a direct pharmacological action of LY307161.

In one study in diabetic patients (H5N-EW-GFFB), a dose-related rise in both supine systolic and supine diastolic blood pressure was observed, which was maximal at 15/11 mm Hg at 450 mcg of LY307161. No rise was demonstrated in standing systolic or standing diastolic blood pressure, and supine blood pressure returned to baseline in approximately 2 hours.

Measurements of antibody titers to LY307161 in diabetic subjects (H5N-EW-GFFB) and IBS patients (GL61-001) prior to exposure to LY307161 and 30 days after the last exposure showed no clinically significant antibody response to LY307161.

Study RP-09-01 was a single-center, randomized, parallel-group, double-blind, placebo-controlled, dose response, PD, and PK study evaluating the effects of ROSE-010 on gastric, intestinal, and colonic transit and gastric volumes in female patients with IBS-constipation (IBS-C). Doses of 30, 100, or 300 mcg ROSE-010 or matching placebo were administered via abdominal SC injection once daily for 3 consecutive days and 1 final day 2 to 10 days later, over a 13-day interval. The results of this study showed that ROSE-010 actually accelerated colonic transit at 48 hours and did not retard colonic transit at the primary colonic transit endpoint at 24 hours. There was no exacerbation of IBS-C bowel symptoms and no significant effect on stool frequency or consistency.

Overall, in the IBS patient populations studied to date there have been no exacerbations of constipation.

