### **7.2 Clinical Efficacy Assessments**

#### **7.2.1 Amount of Food Consumed (Weight and Energy Content)**

The start time of the standardized lunch will be 30 minutes post-dose; start time will be recorded. Subjects will consume as much of the standardized lunch as desired, and food will be weighed prior to and after eating to assess food intake.

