### 2.3.2 Secondary Endpoints

The secondary endpoints are the following:

- Hunger score on a VAS (0 to 100 mm) measured pre-dose; 20 minutes after study drug administration; and 1.5, 2.5, 3.5, 4.5, 5.5, and 6.5 hours after study drug administration.
- Satiety score on a VAS (0 to 100 mm) measured pre-dose; 20 minutes after study drug administration; and 1.5, 2.5, 3.5, 4.5, 5.5, and 6.5 hours after study drug administration.
- Prospective consumption score on a VAS (0 to 100 mm) measured pre-dose; 20 minutes after study drug administration; and 1.5, 2.5, 3.5, 4.5, 5.5, and 6.5 hours after study drug administration.
- Desire to eat score on a VAS (0 to 100 mm) measured pre-dose; 20 minutes after study drug administration; and 1.5, 2.5, 3.5, 4.5, 5.5, and 6.5 hours after study drug administration.
- Palatability (tastiness) score on a VAS (0 to 100 mm) measured at the start of lunch.
- Incidence and severity of nausea on a VAS (0 to 100 mm) measured pre-dose; 20 minutes after study drug administration; and 1.5, 2.5, 3.5, 4.5, 5.5, and 6.5 hours after study drug administration.
- Plasma PK analysis of ROSE-010: maximum plasma concentration ( $C_{max}$ ), time to  $C_{max}$  ( $T_{max}$ ), area under the plasma concentration-time curve (AUC), terminal phase elimination half-life ( $t_{1/2}$ ), and other plasma PK parameters.

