#### 3.6.8 *Other Safety Assessments*

Observed values and change from baseline values nausea scores on a VAS (0 to 100 mm) will be summarized using descriptive statistics for all measured visits and timepoints.

The area under effect (AUE) will also be calculated from time 0 to 6.5 hours (390 minutes) for the nausea scale on Day 1 and Day 7.  $AUE_{0-6.5}$  will be calculated using the trapezoid method. If any observations are missing for the scheduled timepoints for the AUE calculation, the missing values will be imputed using the LOCF method.

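### In the VAS AUE0-6.5, LOCF carries a pre-lunch appetite score past the meal whenever the 1.5 h reading is missing

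*SAP*

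**What the plan says.** SAP 3.5.1.2 computes AUE "from time 0 to 6.5 hours (390 minutes) for each VAS scale, except palatability, on Day 1 and Day 7". It "will be calculated using the trapezoid method", and for any scheduled reading that is absent "the missing values will be imputed using the last observation carried forward (LOCF) method". SAP 3.6.8 applies the same calculation to nausea on the same two days: "the missing values will be imputed using the LOCF method".

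Each scale is "measured pre-dose; 20 minutes after study drug administration; and 1.5, 2.5, 3.5, 4.5, 5.5, and 6.5 hours after study drug administration" (SAP 2.3.2), which makes eight readings. Protocol 7.2.1 fixes the meal: "The start time of the standardized lunch will be 30 minutes post-dose; start time will be recorded". The pre-dose and 20-minute readings therefore precede lunch, and 1.5 h is the first reading after it.

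The LOCF rule makes no exception for the meal, sets no limit on consecutive imputed readings and is not expressly confined to one day. SAP 3.1.5 only refers back to the analysis sections, and no sensitivity analysis is planned for AUE.

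**The concern.** LOCF assumes that nothing relevant has changed since the last reading. Here an eat-as-desired lunch falls between two scheduled readings, and the appetite scales are there to register its effect. Carrying the 20-minute score to 1.5 h treats the subject as if she had not yet eaten.

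The rule also fails at the other end of the profile. If the last readings are missing, the last post-lunch score is held flat while hunger would be expected to return, so hunger AUE comes out too low.

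At stake is the only planned measure that covers the whole 6.5 h profile, in arms of 15, 15 and 10, where one distorted subject is visible in a mean.

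**Working it through.** The documents give no AUE value, VAS mean, SD or missing rate, so there is no plan figure to reproduce. The reading times and lunch time come from the documents; every VAS profile below is an assumption.

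**Trapezoid weights.** An interior reading has weight (next time - previous time)/2; an end reading has half its single interval. With times 0, 0.333, 1.5, 2.5, 3.5, 4.5, 5.5 and 6.5 h:

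- pre-dose: 0.333/2 = 0.167 h
- 20 min: 1.5/2 = 0.75 h
- 1.5 h: (2.5 - 0.333)/2 = 1.083 h, the largest
- 2.5 to 5.5 h: 1.0 h each
- 6.5 h: 0.5 h
- sum: 6.5 h

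**Only the 1.5 h reading missing.** LOCF error = 1.083 × (20-minute score - true 1.5 h score). For assumed hunger drops across lunch of 20, 30, 40, 50 and 60 mm, this is 21.7, 32.5, 43.3, 54.2 and 65.0 mm·h.

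| Assumed profile (mm) | Full AUE | LOCF at 1.5 h | Next post-lunch reading at 1.5 h |
|---|---|---|---|
| Hunger A: 60, 70, 15, 25, 35, 45, 55, 65 | 271.3 | 330.8 (+22%) | 282.1 (+4%) |
| Hunger B: 65, 70, 20, 25, 35, 45, 55, 65 | 277.5 | 331.7 (+20%) | 277.5 + 1.083 × 5 = 282.9 (+2%) |
| Satiety: 25, 20, 80, 72, 62, 52, 42, 33 | 350.3 | 285.3 (-19%) | 350.3 - 1.083 × 8 = 341.7 (-2%) |

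**Longer runs from 1.5 h (hunger B).** With 1.5 and 2.5 h missing, AUE is 376.7 (+36%). With every reading from 1.5 h on missing, it is 454.2 (+64%).

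**Interpolating across lunch is not enough.** For hunger B, a straight line from 20 min to 2.5 h still gives +27.9 mm·h (+10%).

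**Final readings missing (hunger A, from 4.5 h).** Holding 35 mm changes AUE by 1.0 × (35 - 45) + 1.0 × (35 - 55) + 0.5 × (35 - 65) = -45, so 271.3 becomes 226.3 (-17%).

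**One other reading missing (hunger B).** LOCF errs by only -1% to -4%. For a single gap at 3.5, 4.5 or 5.5 h, interpolation has no error on this profile; at 2.5 h it gives +1% against -2% under LOCF.

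**Effect on an arm mean if one subject lacks 1.5 h.** For a 50 mm drop: 54.2/10 = 5.4 or 54.2/15 = 3.6 mm·h. For the 55 mm drop in hunger A: 59.6/10 = 6.0 or 59.6/15 = 4.0 mm·h, which is 2.2% or 1.5% of 271.3.

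**Nausea, 1.5 h missing.**

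- Assumed peak after 20 min (2, 10, 30, 15, 8, 5, 3, 2): 72.3 becomes 50.7 (-30%).
- Assumed peak at 20 min (2, 35, 15, 8, 5, 3, 2, 2): 61.8 becomes 83.5 (+35%).
- Equal 20-minute and 1.5 h scores: no error.

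**The case against.** **Gaps may be rare.** Subjects are confined from Day -1 to Day 8 (Protocol 3.1), and the questionnaires are administered on site in 5-minute windows (Protocol 7.2.2). The appetite AUE uses the Per Protocol set, which requires all doses and evaluable efficacy data. This stands: no missing rate is given, and the percentages above are errors in one subject on assumed profiles. Nausea uses the Safety Analysis Set, so that filter does not protect it.

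**AUE is not the only summary.** A reader might infer that it is. Both sections first plan observed values and changes at every timepoint, and LOCF is specified only for the AUE calculation. Those summaries remain unimputed.

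**The nausea bias has no fixed direction.** A reader might infer that LOCF hides nausea in those worst affected and so favours the active doses. Protocol 1.3 says only that the most frequent adverse events were "nausea and vomiting, which occurred at time to peak concentration", and Protocol 1.1 puts onset within 30 minutes. No human Tmax is stated, so the 20-minute score may lie before or at the peak. Different missingness by dose is plausible, since nausea is described as dose-related, but nothing in the documents establishes it.

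None of this defends the rule itself. Where the 1.5 h appetite reading is absent, LOCF inserts a score from the wrong side of the meal.

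**Conclusion.** The point holds for the appetite scales and follows from the plan's own timetable. When the 1.5 h reading, or a run starting there, is missing, the reading with the most weight takes a pre-lunch value. The direction rests on the ordinary expectation that lunch lowers hunger and raises fullness. The size depends on the assumed drop: 21.7 to 65.0 mm·h per affected subject for drops of 20 to 60 mm, and about 4 to 6 mm·h on an arm mean for one subject with a drop of about 50 to 55 mm. Final gaps pull hunger AUE the other way. For nausea, the supported conclusion is that AUE can be misstated in either direction.

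The reach is limited to descriptive AUE summaries on Days 1 and 7. The per-timepoint summaries and the primary food-intake model are untouched. The change is worth making because the stated rule gives a predictably wrong value and a better one costs almost nothing.

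**What to change.** In SAP 3.5.1.2 and 3.6.8, replace LOCF with these rules, fixed before unblinding:

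- Impute only within the same day, by linear interpolation between observed post-lunch readings.
- Do not carry or interpolate an appetite score across lunch. If only the 1.5 h reading is missing, use the next post-lunch reading.
- Set AUE to missing if the final reading, or two or more consecutive post-lunch readings, are missing.
- Report AUE on complete profiles as a sensitivity summary.
- For nausea, also report the number of subjects with missing readings by arm.

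No fill-in rule is reliable for a missing 1.5 h nausea score. Using the next reading would give 1.083 × (15 - 30) = -16.3 mm·h (-22%) on the later-peak profile and 1.083 × (8 - 15) = -7.6 mm·h (-12%) on the early-peak one. The complete-profile summary and the counts by arm therefore matter most there.

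The SAP should also say what happens when the pre-dose reading is missing, since LOCF then has no earlier reading from that day to carry.

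The cost is SAP wording and a few lines of code, with no new data. The downside is that a few subjects may have no AUE on a given day; the counts and the per-timepoint summaries keep that visible.

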##### *3.5.1.3 Other Efficacy Analysis*

Observed values, change from baseline, and relative change (i.e. percent change) values of body weight and will be summarized using descriptive statistics at all measured visits and timepoints.

### **3.6 Safety Assessment**

Safety analysis will be performed using the Safety Analysis Set.

### 3.6.1 Adverse Events (AEs)

AEs will be captured from the date of informed consent through study completion. All AEs will be coded to system organ class and preferred term using MedDRA version 27.0. Treatment-emergent adverse events (TEAEs) are defined as AEs that start after the first dose of study drug.

An overview of AEs will be provided including counts and percentages of subjects (and event counts) with the following:

- Any Adverse Events
- Any TEAEs (overall and by maximum severity)
- Any study drug related TEAEs (overall and by maximum severity)
- Any serious AEs (SAEs)
- Any treatment-emergent serious AEs (TESAEs)
- Any TEAEs leading to discontinuation of study drug
- Any TEAEs leading to discontinuation of study
- Any AEs leading to death

Counts and percentages of subjects (and event counts) will also be presented by system organ class and preferred term for each of the categories in the overview.

Listings will be presented specifically for SAEs, TEAEs leading to discontinuation of study drug, and TEAEs leading to discontinuation of study.

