### 8.1 Adverse Events

An AE is defined as any untoward medical occurrence in a clinical investigation subject administered a pharmaceutical product, which does not necessarily have a causal relationship with this treatment. An AE can therefore be any unfavorable and/or unintended sign (including a clinically significant abnormal laboratory finding), symptom, or disease temporally associated with the use of an investigational medicinal product, whether or not related to the investigational medicinal product. All AEs, including observed or volunteered problems, complaints, or symptoms, are to be recorded in the appropriate eCRF. The Investigator should update the appropriate eCRF if additional follow-up information becomes available (eg, the AE has subsided, stabilizes, or the condition becomes chronic in nature).

AEs, which include clinical laboratory test results, will be monitored and documented from the time of informed consent until study participation is complete. Subjects should be instructed to report any event that they experience to the Investigator, whether or not they think the event is due to study drug. From the time of informed consent, Investigators should make an assessment for AEs at each visit and record the event in the appropriate AE eCRF.

Wherever possible, a specific disease or syndrome rather than individual associated signs and symptoms should be identified by the Investigator and recorded in the eCRF. However, if an observed or reported sign or symptom is not considered a component of a specific disease or syndrome by the Investigator, it should be recorded as a separate AE in the eCRF. Additionally, the condition that led to a medical or surgical procedure (eg, surgery, endoscopy, tooth extraction, or transfusion) should be recorded as an AE, not the procedure itself.

Any medical condition already present at the time of informed consent should be recorded as medical history and not be reported as an AE unless the medical condition or signs or symptoms present at baseline change in severity, frequency, or seriousness at any time during the study. In this case, it should be reported as an AE.

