### 9.2.2 Analysis of Safety

Safety analysis will be performed using the Safety Analysis Set.

Safety assessments will include injection site reactions, incidence and severity of nausea on a VAS (0 to 100 mm), clinical laboratory parameters, vital signs, ECGs, physical examinations, incidence and severity of treatment-emergent AEs, and C-SSRS.

AEs will be coded using the Medical Dictionary for Regulatory Activities. Concomitant medications will be coded using the World Health Organization (WHO) Drug Dictionary.

Triplicate 12-lead ECG values will be averaged on each timepoint and visit of measurement for analysis purposes.

Absolute and change from baseline values of incidence and severity of nausea scores on a VAS (0 to 100 mm) will be summarized using descriptive statistics for all measured visits and timepoints.

All safety assessments will be summarized using descriptive statistics or counts and percentages as appropriate at all measured visits and timepoints.

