### 2.2 Study Design

#### 2.2.1 Overview

This is a randomized, placebo-controlled, double-blind, parallel-group Phase 2 study evaluating the efficacy, safety, and PK of daily administrations of the GLP-1 analogue ROSE-010 on appetite and food intake in overweight and obese female subjects. The study is planned to include 3 parallel treatment groups, with 40 subjects randomized in a 3:3:2 ratio to receive ROSE-010 99 mcg, ROSE-010 150 mcg, or placebo, respectively, as follows:

- Treatment Group 1: 99 mcg ROSE-010 (15 subjects) administered SC once daily for 7 consecutive days.
- Treatment Group 2: 150 mcg ROSE-010 (15 subjects) administered SC once daily for 7 consecutive days.
- Treatment Group 3: Placebo (10 subjects) administered SC once daily for 7 consecutive days.

For each subject, the study will consist of the following:

- Screening Period (Day -28 to -2) and Check-In (Day -1), during which subjects will be evaluated for eligibility.
- Treatment Period (Day 1 to Day 7), during which subjects will receive 7 once-daily doses of ROSE-010 or placebo, followed by discharge on Day 8.
- Follow-up phone call, which will be completed 7 ( $\pm$ 2) days after the final dose of study drug.

Consenting subjects will be screened for eligibility according to study-specific inclusion/exclusion criteria within 28 days prior to the first administration of study drug (Day 1). Subjects will be admitted to the CPU on Day -1 and will remain confined to the CPU until discharge on Day 8/Early Termination (ET). On Day 1, subjects will be randomized in a 3:3:2 ratio to receive ROSE-010 99 mcg, ROSE-010 150 mcg, or placebo, respectively. Study drug will be administered SC once daily (30 minutes before lunch) for 7 consecutive days (Days 1 to 7). All meals served at the CPU will be standardized and controlled. Subjects will consume as much of the standardized lunch as desired, and food will be weighed prior to and after eating to assess food intake. Assessments of hunger, satiety, prospective consumption, desire to eat, palatability, and nausea will be performed. Blood samples will be collected to evaluate PK. Safety parameters will be monitored.

Subjects will be discharged on Day 8/ET. The end of study follow-up phone call will be completed 7 ( $\pm$ 2) days after the final dose of study drug.

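### The SAP defines treatment-emergent AEs by start date alone, so an AE that begins between consent and first dose and worsens on drug can be left out of the TEAE outputs

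*SAP*

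**What the plan says.** SAP 3.6.1 sets the collection window: "AEs will be captured from the date of informed consent through study completion". It then gives the only definition of treatment emergence in either document: "Treatment-emergent adverse events (TEAEs) are defined as AEs that start after the first dose of study drug". The Protocol uses the term, for example in 9.2.2 ("incidence and severity of treatment-emergent AEs, and C-SSRS"), but does not define it.

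The pre-dose window comes from the design description in SAP 2.2.1: "Screening Period (Day -28 to -2) and Check-In (Day -1), during which subjects will be evaluated for eligibility".

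Two passages in Protocol 8.1 bear on worsening:

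- Conditions that predate consent: "Any medical condition already present at the time of informed consent should be recorded as medical history and not be reported as an AE", with an exception where the condition or "signs or symptoms present at baseline change in severity, frequency, or seriousness at any time during the study". In that case the change is reported as an AE. Appendix A, note w, repeats this.
- Existing AE records: "The Investigator should update the appropriate eCRF if additional follow-up information becomes available".

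The AE overview in SAP 3.6.1 has rows for any AE, TEAEs, related TEAEs, SAEs, TESAEs, TEAEs leading to discontinuation of drug or of study, and AEs leading to death. Each category is repeated by system organ class and preferred term. Only the TEAE and related-TEAE rows are split by maximum severity. On listings: "Listings will be presented specifically for SAEs, TEAEs leading to discontinuation of study drug, and TEAEs leading to discontinuation of study".

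**The concern.** A definition based on onset alone asks when an event began, not whether it got worse under treatment. For an AE already present at first dose, the worsening is the part that could reflect the drug. If a headache starts at Check-In as mild and becomes severe after dosing, its one record has a pre-dose start, and the definition classes the whole event as not treatment-emergent.

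Safety and tolerability is a stated secondary objective. The arms hold 15, 15 and 10 subjects, so a single misclassified subject is visible in a percentage. The SAP does attend to the pre-dose/post-dose boundary elsewhere. A medication started before the first dose and still ongoing is classed as concomitant (3.3.6), and laboratory abnormalities are counted separately before and after the first dose (3.6.2). AEs have no matching rule.

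**Working it through.** The plan states no figure that depends on this definition, so there is none to reproduce. The check traces one case through the text and then sizes it.

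**Traced case.** A subject consents, an AE starts between Day -28 and pre-dose Day 1, and its severity rises after the first dose.

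1. Is it in the AE database? Yes, because collection starts at consent (SAP 3.6.1).
2. Does the Protocol's worsening rule reach it? Not clearly. The sentence in Protocol 8.1 opens with conditions already present at consent, and this AE began later. Even on a broad reading, the rule says only that the change is reported as an AE. It does not say that an AE already on record gets a new entry or a new start date.
3. Is it a TEAE? If it stays one record with its original start date, no. If a new entry is opened at the worsening, the new entry starts after dosing and counts.
4. Where does the single-record case appear?

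| SAP output | Event included? |
|---|---|
| Any AE, overall and by class/term | Yes |
| Any SAE (table and listing), AEs leading to death | Yes, if applicable |
| TEAEs, overall and by maximum severity | No |
| Related TEAEs, overall and by maximum severity | No |
| TESAEs | No |
| TEAEs leading to discontinuation of drug or of study (tables and listings) | No |
| Nausea VAS, laboratory, vital-sign and ECG summaries | Yes, if the worsening is in one of these measures |

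The rows that drop out are the ones in 3.6.1 that carry severity and relatedness. Stopping study drug is a further gap. Protocol 4.3 separates stopping drug from leaving the study, but the disposition table in SAP 3.3.1 gives reasons only for leaving the study.

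**Size.** Arm sizes are from SAP 2.2.1. The two rates are assumptions and appear in neither document.

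- Subjects with an AE ongoing at first dose, assumed 5–15%: 40 × 0.05 = 2; 40 × 0.15 = 6.
- Of these, worsening after dosing, assumed one third: 2 / 3 = 0.67; 6 / 3 = 2. So about 0.7–2 subjects across all three arms.
- Expected in one 15-subject arm: 0.67 × 15/40 = 0.25; 2 × 15/40 = 0.75. As a share of the arm: 0.25/15 = 1.7% to 0.75/15 = 5.0%.
- One whole subject in an active arm: 1/15 = 6.7 percentage points. In placebo: 1/10 = 10.0 points.

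The last two figures apply to any-TEAE incidence only if that subject has no other TEAE.

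**The case against.** The strongest reply is that the loss depends on a recording convention that the documents do not give. A reader might infer that the Protocol orders the worsened AE to be kept under its pre-dose start date. It does not. The sentence on updating the eCRF is illustrated with follow-up and outcome information (the event has subsided, stabilised or become chronic) and is silent on rising severity and on start dates. Protocol 11.4 mentions eCRF completion procedures, and SAP section 6 refers to separate programming specifications. Either could require a new entry at worsening, in which case the present definition already works. This stands, and it is why the point is conditional.

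A reader might also infer that the event disappears from safety reporting. It does not. It keeps its place among all AEs and, if serious, among SAEs. Study withdrawal still appears in disposition with its reason. Nausea has VAS summaries with change from baseline and an AUE on Days 1 and 7 (SAP 3.6.8), and laboratory values have change from baseline and abnormality counts (SAP 3.6.2). Protocol 9.2 also promises listings of individual data. This stands too. What remains exposed is symptoms with no measurement of their own, together with the severity, relatedness and drug-discontinuation tables.

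Third, the phrase about signs or symptoms present at baseline could be read as covering AEs that begin after consent, since baseline is the last assessment before first dose. That reading is arguable, but it does not settle the start date.

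Finally, the case should be uncommon. Subjects must be in good health at Screening and Check-In, most medication is barred for at least 14 days before dosing, eligibility is confirmed before dosing on Day 1, and treatment lasts 7 days. This limits the expected size, not the correctness of the point.

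**Conclusion.** The point holds in conditional form. SAP 3.6.1 has no worsening clause, and nothing else in either document supplies one for AEs that begin between consent and first dose. If such an AE is kept as one record, its worsening on drug is missing from every TEAE-based output, though not from the any-AE and SAE outputs.

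The expected size is small: about 0.7–2 subjects in the whole trial under assumed rates of 5–15% and one third. It would be wrong to present 6.7 points as the expected understatement in an active arm. That is the effect of one whole subject falling in that arm with no other TEAE; the expected share on the same assumptions is 1.7–5.0%. Nor do the documents show that harm will be understated, only that the definition allows it. The change is worth making because it costs little and removes the dependence on an unstated convention.

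**What to change.** In SAP 3.6.1, define a TEAE as an AE that starts, or increases in severity, on or after the first dose of study drug. In the eCRF completion instructions, state that post-dose worsening of a pre-dose AE is entered as a new AE dated at the worsening, or else that the date of the severity change is captured so the definition can be programmed. If the eCRF instructions already require a new entry, the SAP should say that it relies on this.

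The cost is one SAP clause and one eCRF completion instruction. TEAE counts may be slightly higher. No change to design, sample size or assessments is needed.
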